## 7.6 Description of Subgroups to be Analyzed

No subgroup analyses are planned.

## 7.7 Statistical Analysis Methodology

Statistical analysis will be performed using SAS® software Version 9.3 or higher. All continuous variables will be summarized using the following descriptive statistics: n, mean,

standard deviation, median, minimum value, and maximum value. Categorical variables will be summarized using the following descriptive statistics: frequency counts and percentages. All data will be listed in data listings.

Further details of the statistical analyses, methods, and data conventions are described in the SAP. The SAP will be prepared by DaVita Clinical Research and approved by the Sponsor. This document may modify the plans outlined in the protocol; however, any major modifications of the primary analysis will also be reflected in a protocol amendment. Additional statistical analyses other than those described in this section may be performed if deemed appropriate in the plan.

The general principles listed below will be applied throughout the study:

- Unless otherwise stated, continuous data will be summarized with the following descriptive statistics: number of non-missing observations (n), mean, standard deviation (SD), median, minimum, and maximum. For categorical variables, frequencies and percentages of patients will be presented.
- All study data will be included in the individual patient data listings. All summary tables will present descriptive statistics for the parameters to be analyzed, wherever applicable.
- Missing data will not be imputed but will be analyzed as missing.

### **7.7.1 Pharmacokinetic Analysis**

Pharmacokinetic parameter endpoints for KBP-5074 will be calculated, listed, and summarized using descriptive statistics as detailed in the SAP. Pharmacokinetic parameter listings and statistical summaries will be generated separately for each study part. Part 2 PK parameters also will be listed and summarized for the following periods: during the interdialytic interval, during dialysis, and overall.

KBP-5074 concentration data will be listed and summarized by study part and collection time point as detailed in the SAP. Part 2 concentration data will be listed and summarized for the following periods: during the interdialytic interval, during dialysis, and overall.

### **7.7.2 Safety Analyses**

#### Adverse Events

An overall summary of the number and percentage of patients in each category will be presented, as will an overall summary of the number of events in each category. The number and percentage of patients reporting AEs in each category above will be summarized by

cohort and part of the study according to the system organ class (SOC) and preferred term (PT) assigned to the event using MedDRA.

All AE data will be listed for all patients. Both the Investigator's verbatim terms and the MedDRA preferred terms will be listed for each patient. Listings will also include the SAEs, start and end time and date of AEs, relationship to study drug, severity, and action taken for the AEs. A summary of deaths (for all deaths, AE outcome, not AE term, is death) will be provided by number and percentage of patients by cohort.

### Vital Signs

Changes from baseline in vital signs at each scheduled timepoint will be summarized by study part and cohort for the safety population using descriptive statistics (number [n], mean, SD, median, minimum, and maximum). The baseline value is defined as the last value observed prior to first administration of study drug on Day 1. The change from baseline is defined as the post-baseline value minus the baseline value. There will not be any imputation for missing values. All vital sign data will be listed individually by each patient based on the safety population.

### ECGs

A listing will be provided for Investigator-identified ECG abnormalities from safety ECGs. Overall evaluation of safety ECGs will be summarized by study part and cohort using frequency counts and percentage of patients as normal or abnormal, and the relevance of the abnormality will be summarized by "CS" or "NCS".

Continuous ECG parameters including heart rate, ventricular rate, PQ or PR interval, QRS duration, QT interval (uncorrected), and QTcF interval will be summarized for each study part and over each scheduled timepoint in terms of absolute values using descriptive statistics (n, mean, SD, median, minimum, and maximum).

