### 6.1.4 12-Lead Electrocardiograms

Electrocardiogram parameters of ventricular rate, PQ or PR interval, QRS duration, QT interval (uncorrected), and QT interval corrected for heart rate according to Fridericia's formula (QTcF) will be performed at the timepoints specified in [Table 12-1](#) and [Table 12-2](#) for Part 1 and Part 2, respectively.

Electrocardiograms will be obtained with the patient remaining in a semi-recumbent position following 5 minutes of rest. If other procedures are scheduled at the same timepoint, the ECG should be obtained after vital sign measurements and/or before the scheduled blood draw. The allowable window for ECGs to be obtained with respect to their nominal timepoint is -60 minutes for predose ECGs and  $\pm 30$  minutes for postdose ECGs.

For all patients, ECGs will be reviewed, signed, and dated by the Investigator or a qualified designee. The ECGs will be classified as being one of three categories: normal, abnormal but not clinically significant (NCS), or abnormal and CS. All CS findings will be reported as AEs.

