### Physical Examination

Changes in baseline in physical examination findings (Normal, Abnormal-NCS, Abnormal-CS) will be summarized using counts and percentages for each study part and each cohort, and will also be listed individually for each scheduled timepoint.

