### Clinical Laboratory Tests

All laboratory data will be summarized by study part and cohort, and at each scheduled timepoint using descriptive statistics (n, mean, SD, median, minimum, and maximum).

The baseline value is the last value observed prior to first administration of study drug and any information taken after first administration of study drug is regarded as post baseline

information. The change-from-baseline variables will be calculated as the post-baseline value minus the value at baseline. Change from baseline on continuous data will be summarized using descriptive statistics at each scheduled time point by cohort. For categorical data, change-from-baseline will be summarized using frequency and proportion at each scheduled timepoint by cohort.

Individual data listings of laboratory results will be presented for each patient. Values outside of the laboratory's reference range (i.e, those with low or high values) will be flagged in the laboratory listings.

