## **12 Appendices**

### **12.1 Appendix: Schedule of Events**

**Table 12-1 Schedule of Events for Part 1**

Day	Screening	Patients Resident at CRU											Outpatient Visits						EOS 	
	-28 to -2	-1	Day 1 to Day 2											3	4	5	6	8	10	12
Hours		-24	0	2	4	6	8	10	12	18	24	48	72	96	120	168	216	264	312	
Admission to CRU		X																		
Discharge from CRU											X									
Informed Consent	X																			
Eligibility Assessment	X	X																		
Medical History	X																			
Demographics	X																			
Height (cm), Weight (kg), BMI	X																			
Previous Medications	X	X																		
Concomitant Medications			X																	
Physical Examination	X	X 																		X
Single 12-lead ECG 	X		X			X														X
Vital Signs (BP, PR, RR, T) 	X	X	X	X	X	X	X		X		X	X	X	X	X	X	X	X	X	X
AE Assessment	X	X	X																	
Clinical Laboratory Samples 	X	X				X					X 	X 	X 	X 	X 	X 	X 	X 	X 	X
Dose Administration			X																	
PK Blood Samples 			X	X	X	X	X	X	X	X	X	X	X	X	X	X	X	X	X	X
Biomarker Samples  (Aldosterone and Potassium)			X	X		X			X		X	X	X	X	X	X	X	X	X	X
HIV, Hepatitis B and C Screen	X																			
Drug/Alcohol Screen 	X	X 																		
Serum/Urine Pregnancy Test 	X	X																		X

AE= adverse event; BP = blood pressure; CRU = clinical research unit; ECG = electrocardiogram; EOS = end of study; HIV = human immunodeficiency virus; PR = pulse rate; PK = pharmacokinetics; RR = respiratory rate; T = temperature.  
 Note: baseline is the Day 1 predose (time 0) sample.

Brief physical examination will be conducted at Check-in (Day -1).

Patient should be resting in a semi-recumbent position for at least 5 minutes prior to ECG.

Blood pressure, heart rate, respiratory rate and oral temperature will be measured in patients in a semi-recumbent position for at least 5 minutes.

Clinical laboratory samples include: hematology, clinical chemistry, liver function, and urinalysis.

Laboratory samples for only creatinine will be collected at 24, 48, 72, 96, 120, 168, 216, and 264 hours postdose.

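### The ECG paragraph of Section 7.7.2 plans absolute-value summaries for QTcF and the other intervals and no change-from-baseline summary, although a Day 1 predose ECG is collected

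*Protocol*

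**What the plan says.** In Protocol Section 7.7.2, the ECG paragraph lists heart rate, ventricular rate, PQ or PR interval, QRS duration, uncorrected QT and QTcF. These are to be "summarized for each study part and over each scheduled timepoint in terms of absolute values using descriptive statistics", namely n, mean, SD, median, minimum and maximum. The categorical part of that paragraph is also by status and not by shift: "Overall evaluation of safety ECGs will be summarized by study part and cohort using frequency counts and percentage of patients as normal or abnormal", with abnormalities split by clinical significance.

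The neighbouring paragraphs of Section 7.7.2 treat the other safety measures differently:

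- Vital signs: "Changes from baseline in vital signs at each scheduled timepoint will be summarized by study part and cohort for the safety population".
- Physical examination: "Changes in baseline in physical examination findings (Normal, Abnormal-NCS, Abnormal-CS) will be summarized using counts and percentages".
- Laboratory tests: "Change from baseline on continuous data will be summarized using descriptive statistics at each scheduled time point by cohort".

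A baseline ECG exists. Section 6.1.4 says: "The allowable window for ECGs to be obtained with respect to their nominal timepoint is -60 minutes for predose ECGs". The ECG rows of Tables 12-1 and 12-2 show recordings at Screening, time 0, 6 h and end of study (Day 14, 312 h). Both tables carry the note: "Note: baseline is the Day 1 predose (time 0) sample".

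**The concern.** Safety and tolerability is a primary objective (Section 2.1), and ECGs are a named safety assessment (Section 6.1). For a repeated measurement with a predose value, the natural safety question is how far each patient moved from his or her own baseline. A table of absolute values at each timepoint describes the group at that time and does not link a patient's two readings.

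With 6 patients per part, differences between patients can make up most of the spread in such a table, and one sizeable individual change can leave no trace in it. The protocol names a metric for ECGs and names a different one for the other safety measures in the same section, without giving a reason. The point is therefore more than silence on a detail left to the SAP: an SAP that followed the paragraph literally would produce the absolute table and no change table.

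**Working it through.** The protocol gives no QTcF figure, SD or precision target, so there is nothing to reproduce. The check has three parts.

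**1. Text comparison (Section 7.7.2 and schedules)**

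| Measure | Predose value collected | Metric stated in 7.7.2 |
|---|---|---|
| Vital signs | yes | change from baseline |
| Physical examination | yes (Day -1) | change relative to baseline, as counts |
| Laboratory tests | yes | values and change from baseline |
| Continuous ECG parameters | yes (time 0) | absolute values |

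No other section of the protocol plans change from baseline for ECG parameters. The synopsis says only that the safety assessments, ECGs among them, are analysed descriptively.

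**2. What the absolute table can and cannot show (constructed values, n = 6)**

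Predose QTcF in both scenarios: 390, 400, 410, 420, 430, 440 ms; mean 2490/6 = 415.

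- Scenario A: every patient rises by 5 ms. Postdose: 395, 405, 415, 425, 435, 445.
- Scenario B: the first patient rises by 55 ms and the other five fall by 5 ms. Postdose: 445, 395, 405, 415, 425, 435.

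The six postdose numbers are the same, so every planned statistic agrees: mean 420, median 420, minimum 395, maximum 445, and SD = sqrt[2(25² + 15² + 5²)/5] = sqrt(350) = 18.7.

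| Within-patient change (ms) | A | B |
|---|---|---|
| Mean | 5 | (55 - 25)/6 = 5 |
| SD | 0 | sqrt[(50² + 5 × 10²)/5] = sqrt(600) = 24.5 |
| Median | 5 | -5 |
| Minimum | 5 | -5 |
| Maximum | 5 | 55 |

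The mean change equals the difference of the two planned means, 420 - 415 = 5, provided the same patients contribute at both times. The other four statistics depend on how the readings pair up, and the absolute table does not carry that pairing. In this example it places the largest change only between 5 ms (it cannot be below the mean change) and 445 - 390 = 55 ms.

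**3. Precision, as an assumption**

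If the SD is equal at both times and repeat readings in a patient correlate at r, then SD(change)/SD(absolute) = sqrt[2(1 - r)]. The protocol gives no value of r. Over an assumed range:

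- r = 0.5: sqrt(1.0) = 1.00, no reduction
- r = 0.7: sqrt(0.6) = 0.775
- r = 0.8: sqrt(0.4) = 0.632

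Below r = 0.5 the change has the larger SD. The loss of the individual changes in part 2 does not depend on any particular value of r.

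**The case against.** The strongest reply is that the paragraph says what will be summarised and excludes nothing. The vital signs paragraph names change alone, and nobody would take that as barring a table of absolute vital signs. Section 7.2 refers the safety summaries to the SAP, and Section 7.7 lets the SAP modify the plans and add analyses. This stands to the extent that a reader might infer that ECGs will be summarised only as absolute values. The protocol does not say so, and the SAP is not at hand. It does not remove the point, because the protocol does state a metric for ECGs and states a different one for the measures beside it.

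A second reply is that within-patient change does not go unexamined. Section 7.7 puts all study data into individual listings. With 6 patients per part and two scheduled postdose ECGs each, every change is one subtraction away. Under Section 6.1.4 each ECG is classified and clinically significant findings become adverse events. Section 6.1.6.3 extends this to results that worsen from baseline and are judged clinically significant. This also stands: a reader might infer that individual prolongation would be hidden or lost, and the documents do not support that. What these routes do not give is a planned quantitative summary. The adverse event route rests on judgment, and a rise within the normal range could remain normal in the categorical table.

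Third, the practical stakes are low. No QT objective is stated in Section 2, no formal safety analysis is planned, and Section 1.3 reports no clinically meaningful ECG trends in the earlier single-dose study at doses up to 30 mg, against 0.5 mg here. That is fair and limits the weight of the point.

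**Conclusion.** The point holds as a modest reporting gap. Section 7.7.2 specifies absolute-value summaries for continuous ECG parameters and plans no change-from-baseline summary, out of line with its own treatment of vital signs, physical examination and laboratory data. The planned table cannot show the SD, median, minimum or maximum of within-patient change. With complete data, the mean change alone can be derived from it.

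It would go too far to say that ECG change is not analysed at all, that the largest individual change cannot be recovered from the study's output, or that spread is not reported. The listings and adverse event reporting cover the first two in part, and the SD and range of absolute values are planned; the spread of change is what is missing. Nor should a precision gain be claimed as a fact: it rests on an assumed correlation, is nil at 0.5, and is measured against no target in the protocol. The six-patient example is constructed and shows what is possible, not what is expected. No figure or objective in the protocol is wrong because of this point.

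**What to change.** In the ECG paragraph of Section 7.7.2, add a summary of change from the Day 1 predose ECG at 6 h and Day 14 for the parameters already listed there, by study part, with n, mean, SD, median, minimum and maximum. State that the ECG baseline is the Day 1 predose recording, to match the note under Tables 12-1 and 12-2. Include each patient's largest QTcF change in the ECG listing. If the SAP already contains this, aligning the protocol text is enough.

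The cost is one extra table and one extra listing column, from recordings already scheduled. No new procedure, visit or patient is needed.

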### Physical Examination

Changes in baseline in physical examination findings (Normal, Abnormal-NCS, Abnormal-CS) will be summarized using counts and percentages for each study part and each cohort, and will also be listed individually for each scheduled timepoint.

### Clinical Laboratory Tests

All laboratory data will be summarized by study part and cohort, and at each scheduled timepoint using descriptive statistics (n, mean, SD, median, minimum, and maximum).

The baseline value is the last value observed prior to first administration of study drug and any information taken after first administration of study drug is regarded as post baseline

information. The change-from-baseline variables will be calculated as the post-baseline value minus the value at baseline. Change from baseline on continuous data will be summarized using descriptive statistics at each scheduled time point by cohort. For categorical data, change-from-baseline will be summarized using frequency and proportion at each scheduled timepoint by cohort.

Individual data listings of laboratory results will be presented for each patient. Values outside of the laboratory's reference range (i.e, those with low or high values) will be flagged in the laboratory listings.

### **7.7.3 Pharmacodynamic Analyses**

The change from baseline in concentrations of plasma aldosterone and serum potassium after single doses of KBP-5074 will be summarized by study part and cohort, and at each scheduled time point using descriptive statistics (n, mean, SD, median, minimum, and maximum).

The baseline value is the last value observed prior to first administration of study drug and any values after first administration of study drug are regarded as post-baseline values. The change-from-baseline variables will be calculated as the post-baseline value minus the value at baseline.

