**Figure 3-1 Study Design Schematic for Part 1**

Abbreviations: CRU = clinical research unit; PK = pharmacokinetic.

##### Part 2

[figure not shown]
In Part 2, a single cohort (Cohort 2) of 6 HD patients will receive a single dose of 0.5 mg KBP-5074 on the same day of HD (immediately after the HD). Following dosing, patients will be followed for 13 days for PK and safety assessments (see Table 12-2). The PK

samples will be obtained relative to dose administration as follows (All PK samples will be collected within  $\pm 5$  minutes of the nominal time unless otherwise specified):

- During the interdialytic interval (using a venous stick or cannula) immediately predose (at time 0 [-5 min]; collected immediately prior to dosing, but following the termination of a previous dialysis session), 2, 4, 6, 8, 10, 12, 18, and 24 hours postdose;
- During the second HD session at 44 (immediately prior to HD [using a venous stick or cannula; -5 min] and 5 minutes after the start of HD [inlet {arterial;  $\pm 1$  min} and outlet {venous;  $\pm 1$  min} samples]), 44.25, 44.5, 46, and 47 hours postdose, and at the end of the second HD session;
- Following dialysis at 48.5, 49, 50, 52, 72, 96, 120, 168, 216, 264, and 312 hours postdose.

[figure not shown]
A study design schematic for a Monday, Wednesday, Friday (MWF) and Tuesday, Thursday, Saturday (TTS) HD schedule for Part 2 is presented in [Figure 3-2](#) and [Figure 3-3](#), respectively.

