#### **4.1.1 Inclusion Criteria**

Each patient must meet all of the following criteria to be enrolled in this study:

1. Male or female, between 18 and 75 years of age, inclusive.
2. Body mass index (BMI) between 19 and 42 kg/m^2, inclusive.
3. Has severe CKD, defined as eGFR  $\geq 15$  mL/min/1.73 m^2 and  $\leq 29$  mL/min/1.73 m^2 based on the IDMS traceable MDRD equation, according to laboratory results at Screening (non-HD patients only [Part 1]). Patients with a prior history of greater than 2 weeks of dialysis in the past and who have dialyzed in the 6 months prior to dosing on Day 1 will be excluded. Patients who have had temporary dialysis for acute kidney injury will be allowed at the discretion of the Investigator.
4. Serum potassium between 3.3 and 4.8 mmol/L, inclusive, at both Screening and Check-in (Day -1) (non-HD patients only [Part 1]). One repeat test will be allowed to exclude lab error or hemolyzed samples.
5. Is on a hemodialysis schedule for at least 45 days with KT/V  $\geq 1.2$  for end-stage renal disease (ESRD) regardless of the etiology including diabetes, with an average 3 hemodialysis sessions per week (HD patients only [Part 2]).
6. Is a nonsmoker or light smoker (smokes fewer than 10 cigarettes per day). Alcohol addressed in exclusion.

7. Female patients cannot be pregnant or lactating/breast-feeding and will either be postmenopausal (female patients who state they are postmenopausal should have had cessation of menses for >1 year and have serum follicle stimulating hormone [FSH] levels >40 mIU/mL and estradiol <20 pg/mL, surgically sterile (including bilateral tubal ligation, salpingectomy [with or without oophorectomy], surgical hysterectomy, or bilateral oophorectomy [with or without hysterectomy]) for at least 3 months prior to Screening, or will agree to use, from the time of Check-in (Day -1) until 90 days following the last dose of study drug, the following forms of contraception: double-barrier method, hormonal contraceptives, barrier with spermicide, diaphragm or cervical cap with spermicide, intrauterine device, oral, implantable, or injectable contraceptives, or a sterile sexual partner. All female patients will have a negative urine or serum pregnancy test result prior to enrollment in the study.

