### 5.2 Treatments Administered

All doses of KBP-5074 will be administered orally to patients at the CRU. Administration of each dose of study drug will be supervised, verified (see [Section 5.7](#)), and documented according to the CRU's standard operating procedures. The actual date and time of each dose administration will be entered in the eCRF.

In Part 1 of the study, non-HD patients with severe CKD in Cohort 1 will receive a single oral capsule dose of 0.5 mg KBP-5074 with up to 240 mL of room temperature water on Day 1 following a fast between 2 and 4 hours. The exact amount of water consumed will be recorded in the eCRF.

In Part 2 of the study, HD patients with severe CKD will receive a single 0.5 mg oral capsule dose of KBP-5074 with up to 240 mL of room temperature water following a fast between 2 and 4 hours. The exact amount of water consumed with the dose of KBP-5074 will be recorded in the eCRF. The dose of KBP-5074 will be administered on Day 1 immediately following a dialysis session.

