Blood samples for the determination of KBP-5074 concentrations and corresponding PK analysis will be collected at the following time points (All PK samples will be collected within  $\pm 5$  minutes of the nominal time unless otherwise specified): predose (at time 0 [-5 min], collected immediately prior to dosing) and 2, 4, 6, 8, 10, 12, 18, 24, 48, 72, 96, 120, 168, 216, 264, and 312 hours post dose.

Serum and plasma samples for biomarkers (aldosterone and serum potassium) will be collected at the following time points (All biomarker samples will be collected within  $\pm 5$  minutes of the nominal time unless otherwise specified): predose (at time 0 [-5 min], collected immediately prior to dosing) and 2, 6, 12, 24, 48, 72, 96, 120, 168, 216, 264, and 312 hours post dose.

Urine or salivary drug test performed at Screening and Check-in (Day -1).

Alcohol test (via Breathalyzer) is performed at Check-in (Day -1).

For female patients, urine or serum pregnancy test must be negative to enroll in the study. Patients who have a false positive test attributable to their post-menopausal state or kidney disease, as determined by the Investigator, will be allowed to participate.

End-of-study assessment will be performed after PK blood draw on Day 14 or upon withdrawal/dismissal of a patient from the study.

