Patient should be resting in a semi-recumbent position for at least 5 minutes prior to ECG.

Blood pressure, heart rate, respiratory rate and oral temperature will be measured in patients in a semi-recumbent position for at least 5 minutes.

Clinical laboratory samples include: hematology, clinical chemistry, liver function, and urinalysis.

Dosing will be based on the post dialysis weight from the last dialysis session prior to dosing.

Blood samples for the determination of KBP-5074 concentrations and PK analysis will be collected relative to dose administration as follows (All PK samples will be collected within ±5 minutes of the nominal time unless otherwise specified):

- During the interdialytic interval (using a venous stick or cannula) immediately predose (at time 0 [-5 min]; collected immediately prior to dosing, but following the termination of a previous dialysis session), 2, 4, 6, 8, 10, 12, 18, and 24 hours postdose;
- During the second HD session at 44 (immediately prior to HD [using a venous stick or cannula; -5 min] and 5 minutes after the start of HD [inlet {arterial; ±1 min} and outlet {venous; ±1 min} samples]), 44.25, 44.5, 46, and 47 hours postdose, and at the end of the second HD session;
- Following dialysis (using a venous stick or cannula) at 48.5, 49, 50, 52, 72, 96, 120, 168, 216, 264, and 312 hours postdose.

Cumulative dialysate will be collected and weight/volume determined for the following intervals: 44 to 44.5 hours, 44.5 to 45 hours, 45 to 46 hours, 46 to 47 hours, and 47 to 48 hours postdose. The dialysate collection will end at the end of dialysis (rather than at 48 hours) if a patient has dialysis for <4 hours. An additional sample may be collected until the end of dialysis for sessions lasting longer than 4 hours. The cumulative volume of dialysate collected during each interval will be documented. A 25 mL aliquot will be collected at the end of each interval for determination of KBP-5074 concentration.

Serum and plasma samples for biomarkers (aldosterone and serum potassium) will be collected at the following time points (All biomarker samples will be collected within  $\pm 5$  minutes of the nominal time unless otherwise specified): predose (at time 0 [-5 min], collected immediately prior to dosing) and 2, 6, 12, 24, 48, 72, 96, 120, 168, 216, 264, and 312 hours post dose.

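### In Part 2, change in potassium and aldosterone is measured from a just-dialysed sample, so at least 7 of 12 postdose changes mix dialysis phase with drug effect

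*Protocol*

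**What the plan says.** Section 2.2 has a single secondary objective: change from baseline in plasma aldosterone and serum potassium. Section 7.7.3 defines the baseline ("The baseline value is the last value observed prior to first administration of study drug and any values after first administration" being post-baseline), subtracts it from each later value, and summarises the result by study part, cohort and time point. Dialysis is not mentioned.

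For Part 2, Section 5.2 states: "The dose of KBP-5074 will be administered on Day 1 immediately following a dialysis session". Footnote 9 of Table 12-2 sets the biomarker draws: "minutes of the nominal time unless otherwise specified): predose (at time 0 [-5 min], collected immediately prior to dosing) and 2, 6, 12" hours, continuing to 312 hours. These are the same times as for the non-dialysis patients in footnote 7 of Table 12-1: "2, 6, 12, 24, 48, 72, 96, 120, 168, 216, 264, and 312 hours post dose".

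The PK schedule, by contrast, was adapted to dialysis. Section 3.1 adds a sample just before the next session ("During the second HD session at 44 (immediately prior to HD [using a venous stick or cannula; -5 min"), and Section 7.7.1 summarises Part 2 PK by interdialytic, dialysis and overall periods. The PD analysis has no such split.

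Part 2 has no comparator: "In Part 2, a single cohort (Cohort 2) of 6 HD patients will receive a single dose of 0.5 mg KBP-5074".

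**The concern.** A sample drawn minutes after dialysis reflects what the session has just done to the analyte. A sample drawn a day later reflects the time elapsed since then, with or without drug. Subtracting the first from the second at every time point therefore adds the course between sessions to any drug effect.

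If potassium rises between sessions, that rise would be tabulated as change after KBP-5074. Section 1.1 describes a dose-dependent potassium rise with eplerenone, another mineralocorticoid receptor antagonist, so the artefact would resemble a class effect. No direction is claimed for aldosterone. What is at stake is the readability of the only secondary objective in Part 2; Part 1 is unaffected.

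**Working it through.** The protocol gives no figure to reproduce, so the check is a count of hours since the last session ended.

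**Inputs**
- Twelve postdose biomarker times, from footnote 9 of Table 12-2.
- Baseline at time 0, at the end of a session (Section 5.2; Table 12-2).
- Next session at about 44 to 48 h (Section 2.1).
- Dialysis frequency, from inclusion criterion 5: "with an average 3 hemodialysis sessions per week (HD patients only [Part 2".
- The Tuesday, Thursday, Saturday schematic in the Synopsis, with Day 1 a Tuesday. Dialysis falls on Days 1, 3, 5, 8, 10 and 12.
- Assumptions: fixed chair time, fixed weekly schedule, sessions of about 4 h.

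A next session at 44 h means that Day 1 is the first or second session of the week. The first is drawn; the second is not excluded.

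**Session end times (h from dose)**
- First session of the week: -72, 0, 48, 96, 168, 216, 264.
- Second session of the week: -48, 0, 48, 120, 168, 216, 288.

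**Hours since dialysis = draw time minus latest session end**

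| Draw (h) | Day 1 first session | Day 1 second session |
|---|---|---|
| 2 | 2 | 2 |
| 6 | 6 | 6 |
| 12 | 12 | 12 |
| 24 | 24 | 24 |
| 48 | 0 | 0 |
| 72 | 24 | 24 |
| 96 | 0 | 48 |
| 120 | 24 | 0 |
| 168 | 0 | 0 |
| 216 | 0 | 0 |
| 264 | 0 | 48 |
| 312 | 48 | 24 |
| Day -1 (nominal -24) | 48 | 24 |

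Non-zero postdose entries: 7 of 12 (first), 8 of 12 (second).

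**Upper end.** The protocol does not say whether outpatient draws on dialysis days come before or after dialysis. If the 96, 168, 216 and 264 h draws on the drawn calendar come before, the count is 7 + 4 = 11.

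**Gap before the session.** On the drawn calendar the time-0 session follows a 72 h gap. The sessions ending at 48, 96, 216 and 264 h follow 48 h gaps; the one at 168 h follows 72 h. So 1 of 12 draws matches time 0 on both time since dialysis and preceding gap. In the second-session case time 0 follows a 48 h gap, and 48, 168 and 216 h match: 3 of 12.

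**Day -1 as an undosed reference.** 312 - (-24) = 336 h = 2 x 168 h, so 312 h matches Day -1 on both criteria on any fixed weekly schedule. For second-session patients, 24 and 72 h also match Day -1 on time since dialysis (24 h each), but not on the preceding gap (48 versus 72 h). Potassium is in the chemistry panel drawn on Day -1 (Tables 6-1 and 12-2). The biomarker row has no Day -1 aldosterone.

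**Illustration of size, on an assumption that is not in the documents.** Suppose potassium rises linearly by 0.5 to 2.0 mmol/L over 44 h, a slope of 0.0114 to 0.0455 mmol/L per h. With no drug effect, the change from time 0 would be 0.02 to 0.09 at 2 h, 0.07 to 0.27 at 6 h, and 0.27 to 1.09 at a draw 24 h after dialysis.

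**Drug remaining.** Section 1.3 gives an average half-life above 50 h in healthy subjects. Assuming mono-exponential decline with a half-life of 50, 75 or 100 h, the fraction left is 72, 80 or 85% at 24 h, 10, 21 or 31% at 168 h, and 1.3, 5.6 or 11.5% at 312 h. The draws that match on both criteria on the drawn calendar (168 h against time 0, 312 h against Day -1) thus come late in the profile.

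**The case against.** The last value before dosing is a conventional baseline. The objective is descriptive, with six patients, a single dose, no test and no decision rule, and all data are listed. Section 7.7 lets the SAP modify the protocol's plans and requires an amendment only for major changes to the primary analysis. A different reference, a split by phase or a table label could therefore be set in the SAP. This stands, and it limits what must be changed in the protocol. It does not cover collection: an SAP cannot recover aliquots or dialysis times that were never collected.

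A reader might infer that drug effect and dialysis phase cannot be separated at all at the mismatched times. The documents do not support that for potassium: the Day -1 panel gives an undosed value at a similar time since dialysis for 312 h, and for 24 and 72 h in second-session patients. The confounding belongs to changes taken from time 0.

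A reader might also take 7 of 12 as exact, or as seven equal problems. It is a minimum that depends on chair time and session length, and session length varies: "The dialysate collection will end at the end of dialysis (rather than at 48 hours) if a patient has dialysis for <4 hours", and longer sessions are allowed too. Even the 48 h draw may miss the session end. The seven draws are not equal either, since the 2 h mismatch is probably trivial.

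Finally, the available remedy gives few clean comparisons: 312 h is near washout, and the 24 and 72 h comparisons differ in preceding gap. That is a fair limit on the gain, but the cost is also low.

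**Conclusion.** The point holds and should be fixed. Followed as written, Section 7.7.3 reports dialysis-phase differences as change after drug in Part 2. At least 7 of 12 postdose draws are affected on the drawn calendar, 8 if Day 1 is the second session of the week, and up to 11 if the dialysis-day outpatient draws precede dialysis. These counts assume a fixed weekly slot and sessions of about 4 h.

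The size is unknown. The documents give no interdialytic course for either analyte, so it would go too far to conclude that a potassium rise of any stated amount will appear, or that aldosterone is shifted in a given direction. The mmol/L figures above only illustrate how the mismatch grows with time since dialysis. The primary objectives are not touched.

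**What to change.** In the protocol:

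- (a) Record the start and end time of the last dialysis before each Part 2 biomarker draw, and state whether outpatient draws on dialysis days precede or follow dialysis. Actual sample times are already recorded (Section 6.1.5.1).
- (b) Add an aldosterone aliquot at the existing Day -1 draw, and potassium and aldosterone aliquots at the existing 44 h sample before dialysis.
- (c) In Section 7.7.3, present Part 2 changes by dialysis phase. Interpret change from time 0 only for draws taken at or just after the end of a session. Use Day -1 as the reference where time since dialysis is similar: 312 h for all patients; 24 and 72 h for second-session patients; the added 44 h draw for first-session patients only (44 versus 48 h since dialysis). Say where the preceding gap differs. Label the remaining changes as confounded with dialysis phase and show observed values beside them.

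The SAP could carry (c); (a) and (b) must be in the protocol.

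The cost is a few extra aliquots at two existing draws, recorded dialysis times and table labels. The limits should be stated: few matched points among six patients, fewer if first- and second-session patients are mixed; 312 h near washout; and a Day -1 sample that follows the patient's usual diet rather than the standardized meals of confinement (Section 5.9).
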